#### **7.4.2 Analysis of the secondary variable(s)**

The percentage of each symptom of GERD in the symptom questionnaire in Chinese outpatients in Gastroenterology department will be calculated.

The life quality of GERD patients with atypical symptoms before PPI test will be measured via SF-36 questionnaire.

Receiver operating characteristic (ROC) curves will be constructed to identify the sensitivity and specificity of either GERD Q or 4-week PPI test against positive 24-hour pH monitoring or positive endoscopy result in GERD patients with atypical reflux symptoms

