### Objectives

Primary Objective:	Outcome Measure:
To define the primary symptom of GERD in Chinese outpatients in Gastroenterology department	The primary symptoms of GERD in Chinese outpatients in Gastroenterology department defined by 24-hour impedance-pH monitoring, upper endoscopy or proton pump inhibitor test.

Secondary Objective:	Outcome Measure :

 
1. To investigate the symptom distribution of patients who present with symptoms originated from upper gastrointestinal tract and have pathologic esophageal reflux established by 24-hour impedance-pH monitoring, upper endoscopy, or proton pump inhibitor test.
 
2. To evaluate the life quality of patients with atypical GERD symptoms (symptoms except heartburning and regurgitation)
 
3. To investigate the diagnostic value of proton pump inhibitor trial to diagnose GERD with atypical reflux symptoms
 
4. To investigate the predictive value of Gerd Q to diagnose GERD with atypical reflux symptoms with heartburn or regurgitation
 
	
 
1. The percentage of each symptom of GERD in the symptom questionnaire in Chinese outpatients in Gastroenterology department
 
2. The measurement of SF-36 questionnaire of GERD patients with atypical symptoms before PPI test
 
3. The sensitivity and specificity of positive PPI test in patients with atypical reflux symptom
 
4. The concordance rate of Gerd Q with 24-hour pH monitoring in GERD patients with atypical reflux symptoms with heartburn or regurgitation
 

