## **7. STATISTICAL ANALYSES**

### **7.1 Sample size estimate**

Assuming the prevalence of GERD is 30%, 400 completed patients provides a precision (half width of 95% CI) of 0.045 for the estimate of two-sided 95% confidence interval of the primary endpoint..

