### **7.3 Outcome measures for analyses**

Pathologic esophageal acid reflux was defined as the percentage total time for which a pH value < 4 was >4.2 % in the distal esophagus. Then, patients were treated with esomeprazole 20 mg twice daily for 28 days. The symptom scores were measured by the frequency score multiplied by the severity scores of the predominant symptom before and at the end of the treatment, and the “ PPI test ” was defined as positive if the overall scores of the predominant dyspeptic symptom in the fourth week decreased by >50 % compared with those of the baseline. GERD is defined by 24-hour impedance-pH monitoring, upper endoscopy or positive PPI test.

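### ROC curves are the only method given for the accuracy of GerdQ and the PPI test: redundant for the fixed PPI rule, and optimistic for GerdQ if its unstated cut-off is taken from the same patients

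*Combined protocol and SAP*

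**What the plan says.** All places are in the combined protocol and SAP.

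- Section 7.4.2 gives one method for the accuracy of both tests: "Receiver operating characteristic (ROC) curves will be constructed to identify the sensitivity and specificity of either GERD Q or 4-week PPI test". The reference and population follow: "against positive 24-hour pH monitoring or positive endoscopy result in GERD patients with atypical reflux symptoms".
- Section 7.3, and the synopsis under Statistical methods, fix when the PPI test is positive: "overall scores of the predominant dyspeptic symptom in the fourth week decreased by >50 % compared with those of the baseline".
- The Objectives table (synopsis and section 2.2) names secondary outcome 3 as "The sensitivity and specificity of positive PPI test in patients with atypical reflux symptom", and secondary outcome 4 as "The concordance rate of Gerd Q with 24-hour pH monitoring in GERD patients with atypical reflux symptoms with heartburn or regurgitation".
- Section 7.3 also says "GERD is defined by 24-hour impedance-pH monitoring, upper endoscopy or positive PPI test".

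The supplied text gives no GerdQ cut-off, no rule for choosing one, no validation step, and no confidence interval for sensitivity, specificity or AUC. Section 3.1 refers to attached questionnaires, which were not available for this review.

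**The concern.** An ROC curve shows how sensitivity and specificity trade off as a threshold moves. Sensitivity and specificity become single figures only once a threshold is fixed, and 7.4.2 does not say which threshold applies.

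For the PPI test the threshold exists in 7.3, so a curve is unnecessary. The one way it could change the answer is if the percentage fall in score were treated as a continuous marker and a new threshold read off. The result would then describe a different test from the one in outcome 3.

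For GerdQ no threshold is stated. A natural reading of 7.4.2 is that the cut-off comes from the curve and its accuracy is reported in the same patients, which favours the test. Section 7.4.2 also does not mention the concordance rate promised by outcome 4, and its reference adds endoscopy to the pH monitoring that outcome 4 names alone.

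Diagnostic accuracy is the whole content of two of the four secondary outcomes. Two competent analysts could follow the plan and report different thresholds and different figures, neither with an interval.

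**Working it through.** **The plan's own figure.** The only computed figure is the precision in section 7.1: 1.96 × √(0.30 × 0.70 / 400) = 0.0449, which agrees with the stated 0.045. It concerns prevalence and says nothing about the precision of sensitivity or specificity.

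**PPI test: area under a one-point ROC.** The curve joins (0, 0), (1−Sp, Se) and (1, 1). By trapezoids:

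AUC = (1−Sp)·Se/2 + Sp·(Se+1)/2 = (Se+Sp)/2.

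With illustrative Se 0.70 and Sp 0.50, AUC = 0.60. The area holds less information than the pair.

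**PPI test: the analysis population.** Let D be a positive reference (pH monitoring or endoscopy) and T a positive PPI test. Section 7.3 makes GERD = D or T. A GERD patient who is reference-negative must therefore be PPI-positive, so specificity among GERD patients is P(T negative | D negative, GERD) = 0. This takes the acid-exposure criterion in 7.3, the only one given, as the meaning of positive monitoring in both sections.

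Illustration, assuming 30% of 400 are reference-positive:
- 120 positive and 280 negative.
- With a true specificity of 0.50, 280 × 0.50 = 140 are false positives.
- The GERD set is 120 + 140 = 260. Its 140 reference-negatives are all PPI-positive, so specificity is 0/140.

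**GerdQ: optimism from a data-chosen cut-off.** None of these inputs is in the documents; all are assumptions:
- normal scores with equal variance in reference-positive and reference-negative patients, separated by d = √2 × Φ⁻¹(AUC);
- 13 evenly spaced cut-offs from −2.5 to 2.5 + d;
- 30% reference-positive;
- the cut-off that maximises Se+Sp is chosen and evaluated in the same sample.

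Mean apparent minus true Se+Sp at the chosen cut-off, 8,000 replicates per cell:

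| Patients (positive/negative) | AUC 0.6 | AUC 0.7 | AUC 0.8 |
|---|---|---|---|
| 400 (120/280) | 0.033 | 0.022 | 0.015 |
| 200 (60/140) | 0.052 | 0.038 | 0.028 |
| 90 (27/63) | 0.087 | 0.069 | 0.056 |

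Using 14 cut-offs moves each cell by no more than about 0.003. A score cut at every observed value gives more: 0.040 to 0.056 with 400 patients and 0.091 to 0.117 with 100. Sensitivity carries most of the excess (0.023 of the 0.033 in the first cell).

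**Size against sampling error.** For illustrative Se 0.70 and Sp 0.50, the 95% half-width of Se+Sp is:
- 120/280: 1.96 × √(0.21/120 + 0.25/280) = 0.10;
- 27/63: 1.96 × √(0.21/27 + 0.25/63) = 0.21.

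The optimism is smaller than the sampling error, but it always runs in the same direction.

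**The case against.** The strongest reply is that nothing in 7.4.2 says any threshold will be re-chosen. Read with 7.3, the PPI-test curve passes through exactly the pair that outcome 3 asks for, so it is redundant and not biased. That stands. A reader might infer that the plan will move the PPI threshold, but the documents do not support this.

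For GerdQ, a reader might infer that the reported figures will be optimistic. The documents do not establish that either. They state no selection rule, a plotted curve or a table of every cut-off carries no selection bias, and a scoring rule in the questionnaire attachment cannot be excluded. The optimism is conditional on a cut-off chosen from these data.

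It is also tempting to assume that the atypical subgroup is small and the bias therefore near the top of the range. No size is given. Six of the eight entry symptoms listed in section 3.1 are neither heartburn nor regurgitation, so the subgroup could be large. Likewise, the 30% in section 7.1 is a GERD prevalence, and GERD there includes PPI responders. Using it as the reference-positive rate is only a working assumption.

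Finally, these are secondary outcomes in a single-site, unrandomised study, and the primary endpoint is untouched. That limits the weight of the point. It does not remove the missing threshold, the missing intervals, the unanalysed concordance rate or the zero specificity.

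**Conclusion.** The point holds as a cheap improvement. An ROC curve is redundant for the PPI test as defined, and outcome 3 is answered only by sensitivity and specificity at the stated rule. For GerdQ the threshold is missing from the supplied text. If it is taken from the curve in the same patients, Se+Sp is overstated by roughly 0.02 to 0.03 with 400 patients and 0.06 to 0.09 with 90, under the assumed score distribution, cut-offs, AUCs and 30% positive rate. If it is fixed beforehand, there is no such optimism.

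The population restriction matters more for the PPI test than the choice of curve. Among GERD patients as 7.3 defines them, PPI-test specificity is 0 whatever its true value, so adding exact intervals without changing the population would not rescue outcome 3.

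**What to change.** Reword section 7.4.2 as follows.

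1. **PPI test.** Report sensitivity and specificity at the rule already in 7.3, with exact (Clopper-Pearson) 95% CIs, in all tested patients with atypical symptoms and not only those classed as GERD. For scale, 84/120 gives 0.61 to 0.78, and 21/30 gives 0.51 to 0.85.
2. **GerdQ.** State the cut-off before analysis, or cite the attachment if it is there. Report sensitivity and specificity, and the concordance rate with pH monitoring that outcome 4 names, each with a 95% CI. If the cut-off is taken from the curve instead, report bootstrap optimism-corrected sensitivity and specificity.
3. **Alignment.** Reconcile the reference and population in 7.4.2 with those in outcome 4.
4. **ROC.** Keep AUC with a 95% CI as a descriptive result.

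The cost is SAP wording and a little more analysis work. No extra patients or measurements are needed, and no clinical rule changes. The accuracy figures may come out slightly less favourable.

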### 2.2 Secondary objectives

Secondary Objective:	Outcome Measure :

 
1. To investigate the symptom distribution of patients who present with symptoms originated from upper gastrointestinal tract and have pathologic esophageal reflux established by 24-hour impedance-pH monitoring, upper endoscopy or proton pump inhibitor test.
 
2. To evaluate the life quality of patients with atypical GERD symptoms (symptoms except heartburning and regurgitation)
 
3. To investigate the diagnostic value of proton pump inhibitor trial to diagnose GERD with atypical reflux symptoms
 
4. To investigate the predictive value of Gerd Q to diagnose GERD with atypical reflux symptoms with heartburn or regurgitation
 
	
 
1. The percentage of each symptom of GERD in the symptom questionnaire in Chinese outpatients in Gastroenterology department
 
2. The measurement of SF-36 questionnaire of GERD patients with atypical symptoms before PPI test
 
3. The sensitivity and specificity of positive PPI test in patients with atypical reflux symptom
 
4. The concordance rate of Gerd Q with 24-hour pH monitoring in GERD patients with atypical reflux symptoms with heartburn or regurgitation
 

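### The GerdQ secondary objective has different measures, reference standards and population wordings in the objectives and in Section 7.4.2, so its result depends on which text is followed

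*Combined protocol and SAP*

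**What the plan says.** Secondary objective 4 reads "To investigate the predictive value of Gerd Q to diagnose GERD with atypical reflux symptoms with heartburn or regurgitation" (Section 2.2, and the same in the synopsis). The outcome paired with it in both places is "The concordance rate of Gerd Q with 24-hour pH monitoring in GERD patients with atypical reflux symptoms with heartburn or regurgitation".

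Section 7.4.2 plans something else. There, ROC curves are to yield sensitivity and specificity, comparing "either GERD Q or 4-week PPI test against positive 24-hour pH monitoring or positive endoscopy result in GERD patients with atypical reflux symptoms". That section does not mention a concordance rate or a predictive value.

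Two other statements bear on the point. Secondary objective 2 refers to "atypical GERD symptoms (symptoms except heartburning and regurgitation", which is the only explanation of the term atypical in the plan. Section 7.3 gives the case definition: "GERD is defined by 24-hour impedance-pH monitoring, upper endoscopy or positive PPI test".

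**The concern.** The two texts set different rules for the same objective, and nothing ranks one above the other. This is more than missing detail: an analyst following Section 2.2 and an analyst following Section 7.4.2 would use different reference standards and report different statistics, possibly in different patients.

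A reader of the final report could not tell whether a GerdQ figure was the one planned. Measure, reference and population would also remain open when the data are seen. Neither text names the statistics that the objective asks for, since predictive value ordinarily means PPV and NPV.

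**Working it through.** **The plan's own figure.** The only sample-size statement is "Assuming the prevalence of GERD is 30%, 400 completed patients provides a precision (half width of 95% CI) of 0.045" (Section 7.1). Check: 1.96 × √(0.30 × 0.70 / 400) = 0.0449, which agrees. It concerns the primary endpoint and is not in dispute. No precision target is given for GerdQ.

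**The texts side by side.**

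| Element | Synopsis Objectives and Section 2.2 | Section 7.4.2 |
|---|---|---|
| Measure | Predictive value (objective); concordance rate (outcome) | ROC curve, sensitivity, specificity |
| Reference | pH monitoring alone | pH monitoring or endoscopy |
| Population | GERD, atypical symptoms, with heartburn or regurgitation | GERD, atypical symptoms, no such qualifier |

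**Who changes class.** Patients positive on pH are reference-positive under both texts. Patients negative on both tests are reference-negative under both. Patients positive on endoscopy and negative on pH are reference-negative under Section 2.2 and reference-positive under Section 7.4.2.

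**Why concordance is a poor summary here.** Concordance = p × Se + (1 − p) × Sp, where p is the share of reference-positives. With assumed Se = 0.50 and Sp = 0.85:
- p = 0.30: 0.30 × 0.50 + 0.70 × 0.85 = 0.745
- p = 0.35: 0.35 × 0.50 + 0.65 × 0.85 = 0.7275

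The instrument is unchanged, yet the figure moves by 0.0175.

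**Illustration of the reference choice.** All cell counts and GerdQ positivity rates are assumed. Take 30% of 400 = 120 GERD patients, of whom 40 are positive on the PPI test only and 80 on pH or endoscopy. Of the 80, let 10, 20 or 30 be endoscopy-positive and pH-negative, which leaves 70, 60 or 50 pH-positive.

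Case A: GerdQ is positive in 70% of the 80 and in 50% of the 40.
- Concordance with pH alone: (70 × 0.7 + 10 × 0.3 + 40 × 0.5) / 120 = 0.600; with 20 and 30 in the discordant cell, 0.567 and 0.533.
- Agreement with pH or endoscopy: (80 × 0.7 + 40 × 0.5) / 120 = 0.633 throughout.
- Sensitivity is 0.70 under either reference. Specificity against pH alone is (10 × 0.3 + 40 × 0.5) / 50 = 0.46, then 0.43 and 0.41. Against pH or endoscopy it is 20 / 40 = 0.50.

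Case B, meant to resemble patients without heartburn or regurgitation: GerdQ is positive in 20% of the 80 and in 10% of the 40.
- Concordance with pH alone: (70 × 0.2 + 10 × 0.8 + 40 × 0.9) / 120 = 0.483, then 0.533 and 0.583.
- Agreement with pH or endoscopy: (80 × 0.2 + 40 × 0.9) / 120 = 0.433.
- Sensitivity is 0.20 under either reference. Specificity is 0.88 to 0.86 against pH alone, and 36 / 40 = 0.90 against pH or endoscopy.

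Switching the reference moves agreement by 0.033 to 0.100 in Case A and by 0.050 to 0.150 in Case B. The population matters more: sensitivity is 0.70 in one case and 0.20 in the other.

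**The GERD restriction.** Both texts analyse GERD patients only. By Section 7.3, such a patient is positive on pH, endoscopy or the PPI test. Against the Section 7.4.2 reference, the only reference-negatives left are patients positive on the PPI test alone. A specificity computed in them says nothing about patients without GERD.

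**The case against.** The strongest reply is that the population difference may be shorthand. Section 7.4.2 covers the PPI test and GerdQ in one sentence and uses one phrase for both, while the objective 4 population is stated twice in identical words. That has some force, and population is the weakest of the three differences. It does not touch the measure or the reference standard, which cannot be read as the same thing.

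A reader might go further and infer that the objective 4 population is empty, because atypical excludes heartburn and regurgitation. The documents do not support this. Objective 2 describes symptoms, not patients free of the typical ones. Section 3.1 lists eight symptoms, and a patient may have several. Atypical symptoms accompanied by heartburn or regurgitation can simply mean patients with both kinds. The wording is ambiguous, and no more than that is shown.

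A reader might also infer a large numerical effect. With the assumed Se and Sp above, concordance would fall from 0.745 to 0.643 if the reference-positive share rose from 30% to 59%, but nothing in the documents supports a share of 59%. The 30% is the assumed prevalence of GERD by the composite definition, so 120 of 400 is not a count of pH-positives. Nor is 400 the denominator for a GERD subgroup. Even if 20 of 400 patients changed class, the share would go only from 30% to 35%, a change of 0.0175.

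It is also fair to say that this is one of four secondary objectives, with no hypothesis test attached, and that nothing shows anyone has chosen or would choose an analysis after seeing the data.

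**Conclusion.** The inconsistency is real and stands in the current text. Measure and reference standard conflict outright between Section 2.2 (with the synopsis) and Section 7.4.2, the population wording differs and is ambiguous, and no section says which text governs. The reported GerdQ result therefore depends on which text is followed.

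The size cannot be derived from the documents. The movement of 0.03 to 0.15 from the reference choice rests entirely on assumed cell counts and GerdQ positivity rates, and it treats all 120 expected GERD patients as the analysis group, which is an upper limit. The direction of the change also depends on those assumptions: agreement rises in Case A and falls in Case B.

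The sponsor should correct this, but it is confined to a secondary objective. The primary endpoint and its stated precision are unaffected.

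**What to change.** Put one specification in the synopsis Objectives, Section 2.2 and Section 7.4.2:

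- **Population:** all enrolled patients who have at least one other symptom plus heartburn or regurgitation, expressly not restricted to those already classed as GERD. Because the only analysis set (Section 7.2.1) is per-protocol completers, say in words that it does not limit this analysis.
- **Reference:** positive pH monitoring or positive endoscopy, as in Section 7.4.2, without the PPI test. Section 7.3 treats endoscopy as sufficient for GERD, so counting an endoscopy-positive patient as reference-negative would sit badly with the plan's own case definition.
- **Measures:** sensitivity and specificity with 95% CIs at a GerdQ cut-off fixed before analysis, the ROC curve, and PPV and NPV because the objective speaks of predictive value. The text reviewed states no cut-off; the questionnaire attachment was not part of it.
- **Supportive:** concordance with pH monitoring alone.

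No new procedure is needed if both tests are done in everyone at screening, as Section 4 requires; the synopsis statistical methods join the two tests with an or, and that wording should be aligned.

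The cost is a wording amendment, with the prospective ethics approval that Section 9.2 requires, and concordance ceases to be the headline figure for this objective. Edition 2.0 is dated June 2018 and the last subject was expected in September 2018, so the specification should be fixed before the GerdQ data are analysed.

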### **Statistical methods**

Assuming the prevalence of GERD is 30%, 400 completed patients provides a precision (half width of 95% CI) of 0.045 for the estimate of two-sided 95% confidence interval of the primary endpoint. All patients underwent upper endoscopy or an ambulatory 24-h pH monitoring. Pathologic esophageal acid reflux was defined as the percentage total time for which a pH value < 4 was >4.2 % in the distal esophagus. Then, patients were treated with esomeprazole 20 mg twice daily for 28 days. The symptom scores were measured by the frequency score multiplied by the severity scores of the predominant symptom before and at the end of the treatment, and the “ PPI test ” was defined as positive if the overall scores of the predominant dyspeptic symptom in the fourth week decreased by >50 % compared with those of the baseline.

Clinical Study Protocol  
Drug Substance Esomeprazole  
Study Code D9612L00157  
Edition 2.0  
Date Jun 8 2018

GERD is defined by either 24-hour impedance-pH monitoring or positive PPI test or positive result from endoscopy. The percentage of each symptom of GERD in the symptom questionnaire in Chinese outpatients in Gastroenterology department will be calculated. The symptom of the highest percentage will be the primary symptom.

	PAGE
TITLE PAGE .....	1
PROTOCOL SYNOPSIS.....	2
TABLE OF CONTENTS.....	5
1. INTRODUCTION .....	7
1.1 Background and rationale for conducting this study .....	7
1.2 Rationale for study design, doses and control groups.....	8
1.3 Study Design .....	9
2. STUDY OBJECTIVES.....	10
2.1 Primary objective .....	10
2.2 Secondary objectives.....	10
2.3 Safety objectives .....	10
3. SUBJECT SELECTION, ENROLMENT, RANDOMISATION, RESTRICTIONS, DISCONTINUATION AND WITHDRAWAL.....	10
3.1 Inclusion criteria .....	11
3.2 Exclusion criteria .....	11
3.3 Subject enrolment and randomization.....	11
3.4 Methods for assigning treatment groups .....	11
3.5 Methods for ensuring blinding.....	11
3.6 Criteria for withdrawal.....	12
3.7 Discontinuation of the study .....	12
4. STUDY PLAN AND TIMING OF PROCEDURES.....	12
4.1 Enrolment/screening period .....	15
4.2 Treatment period.....	15
4.3 Follow-up period.....	15
5. SAFETY REPORTING AND MEDICAL MANAGEMENT .....	15
5.1 Definition.....	15
Adverse Events.....	15
Serious Adverse Event.....	15
Adverse Drug Reaction (ADR) .....	16

5.2	Reporting of Serious Adverse Events.....	16

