heartburn symptoms would underestimate the prevalence of GERD. The last and also the most important reason might lie in that the symptoms which indicate reflux were different in Chinese population. In other words, heartburn might not be the primary reflux symptom in China. For example, more symptoms originated from the upper gastrointestinal tract was described as reflux symptom when patients went to see doctors in China. According to the investigation in our own center, about one third of dyspepsia patients without reflux symptoms presented pathologic esophageal acid reflux in our clinic. Thus heartburn was not understood as well as in other western countries, the symptoms of GERD might distribute differently in China compared to other western countries. So it is necessary to investigate the primary symptoms and spectrum of GERD in Chinese population in order to better define and diagnose GERD.

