### **3.7 Discontinuation of the study**

Those patients who had not symptom relief after four weeks of esomeprazole would discontinue this study.

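### Section 7.4.2 measures PPI-test accuracy only in GERD patients, yet a positive PPI test alone makes a patient GERD, so specificity at the >50% cut-off is 0% by construction if one pH rule applies throughout

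*Combined protocol and SAP*

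**What the plan says.** - **Accuracy analysis (section 7.4.2).** ROC curves are to give the sensitivity and specificity of GerdQ and of the 4-week PPI test "against positive 24-hour pH monitoring or positive endoscopy result in GERD patients with atypical reflux symptoms".
- **Definition of GERD.** Section 7.3: "GERD is defined by 24-hour impedance-pH monitoring, upper endoscopy or positive PPI test". The synopsis (Statistical methods) has the same three-way rule: "GERD is defined by either 24-hour impedance-pH monitoring or positive PPI test or positive result from endoscopy".
- **Positivity rules.** Section 7.3: "Pathologic esophageal acid reflux was defined as the percentage total time for which a pH value < 4 was >4.2" %. The PPI test is positive when the predominant symptom score has fallen by more than 50% at week 4. No separate criterion for impedance appears.
- **Secondary outcome 3 (synopsis and section 2.2).** "The sensitivity and specificity of positive PPI test in patients with atypical reflux symptom", with no restriction to GERD.
- **Secondary outcome 4 (same places).** "The concordance rate of Gerd Q with 24-hour pH monitoring in GERD patients with atypical reflux symptoms", further limited to those with heartburn or regurgitation. Here the GERD restriction is explicit, and the reference is pH monitoring alone.
- **Who remains in the data.** Section 3.7: "Those patients who had not symptom relief after four weeks of esomeprazole would discontinue this study". Section 7.2.1 analyses only per-protocol completers.

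**The concern.** Specificity is the proportion of reference-negative patients whom the index test correctly calls negative. Here the index test helps to decide who is analysed. A patient with negative pH monitoring, negative endoscopy and no PPI response is the true negative that specificity has to count, and that patient is not GERD and so falls outside the set in 7.4.2.

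An analyst who follows 7.4.2 rather than outcome 3 would report a specificity for secondary objective 3 that says nothing about the PPI test, and an ROC curve built on a selected control group. GerdQ is affected differently. Its controls would be PPI responders only (same condition on the pH rule), so the results for objective 4 would not describe patients without GERD.

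**Working it through.** **The plan's own figure.** Section 7.1 gives a half-width of 0.045 for 30% prevalence and 400 completers: 1.96 × √(0.3 × 0.7 / 400) = 0.0449. It reproduces, but has no bearing on this point. The plan states no expected sensitivity or specificity.

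**Step 1. Enumeration, one pH rule throughout.** GERD = pH+ or endoscopy+ or PPI+. Reference-positive = pH+ or endoscopy+. The eight result patterns reduce to four groups:

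| Reference | PPI test | Cell | GERD, so in the 7.4.2 set? |
|---|---|---|---|
| + | + | true positive | yes |
| + | − | false negative | yes |
| − | + | false positive | yes |
| − | − | true negative | **no** |

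Specificity = TN/(TN + FP) = 0/(0 + FP) = 0% for any prevalence or accuracy, and 0/0 if no patient is GERD by PPI test alone. Sensitivity is unchanged, because every reference-positive patient is GERD.

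**Step 2. Size under one pH rule.** Assumptions: one third reference-positive, borrowed from section 1.1 ("about one third of dyspepsia patients without reflux symptoms presented pathologic esophageal acid reflux in our clinic"); 400 or 200 patients with atypical symptoms (number not given); true specificity 50%, 70% or 80%. Intervals are exact (Clopper-Pearson).

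| Patients (reference-negative) | True specificity | All patients, 95% CI | 7.4.2 as written |
|---|---|---|---|
| 400 (267) | 50% | 134/267, 44.0–56.3% | 0/133 |
| 400 (267) | 70% | 187/267, 64.2–75.5% | 0/80 |
| 400 (267) | 80% | 214/267, 74.9–84.8% | 0/53 |
| 200 (133) | 50% | 66/133, 40.8–58.4% | 0/67 |
| 200 (133) | 70% | 93/133, 61.4–77.6% | 0/40 |
| 200 (133) | 80% | 106/133, 71.9–86.2% | 0/27 |

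The all-patient half-width is 5 to 9 percentage points, or 4.5 to 9.7 if the reference-positive share is varied from 20% to 45%.

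**Step 3. A separate impedance rule.** Let q be the share of reference-negative, PPI-negative patients who count as GERD by impedance alone, and s the true specificity. The 7.4.2 estimate is qs/(qs + 1 − s). For example, q = 0.10 and s = 0.7 give 0.07/(0.07 + 0.30) = 19%.

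| Assumed q | s = 50% | s = 70% | s = 80% |
|---|---|---|---|
| 5% | 5% | 10% | 17% |
| 10% | 9% | 19% | 29% |

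**Step 4. ROC curve, one pH rule.** Simulation with assumed normal score reductions, SD 30 points, capped at 100%, 400,000 per group. Group means are set to give the stated accuracy at >50%, and the GERD-only controls are those with a reduction above 50%. AUCs, for true specificity 50%, 70% and 80% in turn:

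| Sensitivity | All patients | GERD patients only |
|---|---|---|
| 70% | 0.64, 0.77, 0.83 | 0.42, 0.47, 0.50 |
| 80% | 0.72, 0.83, 0.88 | 0.52, 0.58, 0.61 |

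**Step 5. GerdQ.** Assumptions: specificity 65% in all reference-negative patients, of whom 20% to 50% respond to PPI. Specificity among the responders is then 73–77% if the odds ratio between GerdQ positivity and PPI response is 0.5, 65% if it is 1, and 52–57% if it is 2. The bias can go either way, and is nil if the two are unrelated.

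**The case against.** The strongest reply is that outcome 3 already names the right population, so 7.4.2 is one loose sentence that may have carried over the restriction from outcome 4, or used GERD to mean suspected GERD. On this view an analyst would notice a specificity of 0% at once. It is true that outcome 3 is worded correctly and that the harm arises only if 7.4.2 is followed. But 7.4.2 is the only description of the accuracy analysis, GERD has an explicit definition in 7.3 and the synopsis, and nothing in the text supports the reading as suspected GERD. Nor would the error always be obvious: with a separate impedance rule the result is a low but plausible-looking figure.

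These limits stand:

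- The exact 0% needs one shared pH rule and the >50% cut-off. At stricter ROC cut-offs specificity can exceed 0; at looser ones it stays 0. The GERD definition refers to impedance-pH monitoring and the reference to pH monitoring, so a separate rule cannot be excluded.
- The one-third share describes acid reflux in dyspepsia patients without reflux symptoms, whereas the reference here also includes endoscopy. The spread, sensitivity, impedance shares and GerdQ inputs are illustrative and have no source in the documents. Step 1 uses none of them.
- The GerdQ point is weaker, since its direction is unknown. Dropping the GERD restriction there changes a stated outcome, although objective 4 concerns prediction of the diagnosis and that requires patients without it.

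**Conclusion.** The concern holds and must be fixed before analysis. With the one pH rule that the plan gives, the PPI-test specificity in 7.4.2 is fixed at 0% (or undefined) at the >50% cut-off, and no sample size can repair it. The same data analysed in all patients with atypical symptoms would estimate specificity to within about 5 to 9 points under the assumptions of step 2. If impedance has its own rule, the estimate is not exactly 0% but remains far too low for the shares tried. The cross-table and the conflict with outcome 3 are certain; the sizes in steps 2 to 5 are illustrations. The damage is confined to the specificity and ROC curve for secondary objective 3 and, with unknown direction, to GerdQ under objective 4. The primary analysis in 7.4.1 is not touched.

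**What to change.** 1. **Section 7.4.2, population.** Replace the restriction to GERD patients by: all patients with atypical reflux symptoms who have the index and reference tests, regardless of final GERD classification. Say whether reference-negative requires both pH monitoring and endoscopy to be negative.
2. **Section 7.4.2, reporting.** Give PPI-test sensitivity and specificity at >50% with exact 95% confidence intervals beside the ROC curve.
3. **Outcome 4 (synopsis and section 2.2).** Change the GerdQ population from GERD patients to all patients with the relevant symptoms, and state one reference standard: it is pH alone in outcome 4, but pH or endoscopy in 7.4.2.
4. **Section 7.3.** State whether impedance has its own positivity criterion or only the >4.2% acid rule applies.
5. **Section 7.2.** Add a diagnostic-accuracy set that keeps the week-4 scores of patients who discontinue under section 3.7. Otherwise 3.7 and the completer set in 7.2.1 could again remove PPI-negative patients.
6. **Who has each test.** Reconcile the passages. The synopsis has endoscopy or pH monitoring, while section 4 has both at screening. Section 1.2 gives esomeprazole to patients without a positive pH finding, whereas section 3.4 assigns it by endoscopy result, and section 7.3 describes treatment without either limit.

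The cost is one phrase in 7.4.2 (outcome 3 already words the population) with a clarifying sentence and a reporting line, matching words in outcome 4, a sentence in 7.3, one analysis set and the reconciliation. No new visit is needed, because both study plans (Tables 1 and 2) schedule a questionnaire at week 4. The sponsor should confirm that it yields the frequency-by-severity score that the PPI test uses.
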